9.2. Registration of Subjects

Subjects will be registered at Day 1, after all baseline assessments have been completed and after the Investigator has verified that the subjects are eligible per criteria in Sections 8.1 and 8.2. No subject may begin treatment prior to assignment of a unique identification number (registration). Any subject identification numbers that are assigned will not be reused even if the subject does not receive treatment.

Refer to the Study Reference Guide for details on registration.

9.3. Blinding Procedures

Not applicable.

CONFIDENTIAL

The information contained herein may not be used, disclosed, or published without the written consent of
Biogen MA Inc.

10. DISCONTINUATION OF STUDY TREATMENT AND/OR WITHDRAWAL OF SUBJECTS FROM THE STUDY

10.1. Discontinuation of Study Treatment

A subject *must* permanently discontinue BG00012 for any of the following reasons:

- The subject becomes pregnant. Study treatment must be discontinued immediately. Report the pregnancy according to the instructions in Section [15.4.1](#).
- The subject experiences a medical emergency that necessitates permanent discontinuation of study treatment.
- The subject has lymphocyte count $<500/\text{mm}^3$ for 6 months as outlined in [Table 4](#) and [Table 5](#).
- The subject experiences a protocol-specified change in laboratory values that necessitates permanent discontinuation of treatment as outlined in [Table 3](#) and [Table 4](#).
- The subject cannot tolerate study treatment.
- The subject receives any of the disallowed concomitant medications for this study.
- The subject or subject's parent/legal guardian desires to discontinue treatment.
- At the discretion of the Investigator for medical reasons or for noncompliance.

The reason for discontinuation of study treatment must be recorded in the subject's eCRF.

Subjects who discontinue treatment may remain in the study and continue protocol-required tests and assessments.

10.2. Withdrawal of Subjects From Study

Subjects must be withdrawn from the study for any one of the following reasons:

- The subject or the subject's parent/guardian withdraws consent.
- The subject enrolls into another interventional clinical study.
- The subject is unwilling or unable to comply with the protocol.

The reason for the subject's withdrawal from the study must be recorded in the subject's eCRF.

CONFIDENTIAL

The information contained herein may not be used, disclosed, or published without the written consent of
Biogen MA Inc.

11. STUDY TREATMENT USE

11.1. Regimen

BG00012 will be taken orally at a dose of 240 mg BID.

Subjects will be instructed to swallow each BG00012 capsule whole and not chewed. The capsule and its contents are not to be crushed, divided, dissolved, sucked, or chewed since the enteric coating of the microtablets in the capsule helps to prevent irritant effects on the stomach. If unable to swallow the capsule, the capsule may be opened and the contents mixed with food immediately prior to consumption.

Refer to and follow the Directions for Handling and Administration (DHA).

11.2. Modification of Dose and/or Treatment Schedule

11.2.1. Dosing Interruption for Abnormal Laboratory Values

BG00012 must be temporarily withheld and/or permanently discontinued when any of the following laboratory values meet the threshold limits defined in [Table 3](#) (laboratory abnormalities that require immediate and permanent discontinuation of study treatment are also specified in [Table 3](#)).

Table 3: Laboratory Criteria Requiring Withholding or Permanent Discontinuation of Treatment

Laboratory Parameter	Laboratory Result	Required Action
AST (SGOT) or ALT (SGPT)	$>3 \times \text{ULN}$	The Investigator should repeat the test as soon as possible. If the retest value confirms AST or ALT $>3 \times \text{ULN}$, then the study treatment must be withheld. If the value remains $>3 \times \text{ULN}$ for ≥ 4 weeks after discontinuation of study treatment, then the subject must permanently discontinue study treatment, and the event must be recorded as an AE .
Creatinine	$>1.2 \times \text{ULN}$	The Investigator should repeat the test as soon as possible. If the retest value confirms that creatinine is $>1.2 \times \text{ULN}$, then the study treatment must be withheld. If the value remains $>1.2 \times \text{ULN}$ for ≥ 4 weeks after discontinuation of study treatment, then the subject must permanently discontinue study treatment, and the event must be recorded as an AE .

CONFIDENTIAL

The information contained herein may not be used, disclosed, or published without the written consent of
Biogen MA Inc.

Laboratory Parameter	Laboratory Result	Required Action
WBC	<2000/mm ³	The Investigator should repeat the test as soon as possible. If the retest value confirms that WBC count is <2000/mm ³ , then the study treatment must be withheld. If the value remains <2000/mm ³ for ≥ 4 weeks after discontinuation of study treatment, then the subject must permanently discontinue study treatment, and the event must be recorded as an AE.
Urinalysis	Positive hematuria on microscopy	The Investigator should repeat the test as soon as possible. If retest confirms microscopic hematuria without known etiology, then the study treatment must be withheld, and urine cytology performed. If hematuria persists for ≥ 4 weeks after discontinuation or if cytology is positive for malignant cells, then the subject must permanently discontinue study treatment, and the event must be recorded as an AE. Subjects should be referred to a nephrologist for further investigation.

AE = adverse event; ALT = alanine transaminase; AST = aspartate transaminase; SGOT = serum glutamic oxaloacetic transaminase; SGPT = serum glutamic pyruvic transaminase; ULN = upper limit of normal; WBC = white blood cell.

[Table 4](#) describes the management of lymphocytes <LLN for subjects during and after study treatment.

CONFIDENTIAL

The information contained herein may not be used, disclosed, or published without the written consent of
Biogen MA Inc.

Table 4: Management of Lymphocyte Count <LLN

Laboratory Parameter	Laboratory Result	Required Action
Lymphocyte count on study treatment	<LLN	The Investigator should repeat the test within 2 weeks. If retest confirms that lymphocyte count is <LLN, lymphocyte count should be closely monitored (at least every 4 weeks).
Lymphocyte count on study treatment	<500/mm ³	If lymphocyte count is <500/mm ³ for more than 6 months, study treatment must be permanently discontinued.
Lymphocyte count in subjects who complete, temporarily withhold, or permanently discontinue BG00012 for any reason	<LLN	Subjects will be followed at least every 4 weeks for 24 weeks and then every 3 months (unless clinically indicated more often or at the Investigator's discretion) until the lymphocyte count is \geq LLN ¹ or for 52 weeks after the last dose, or until one of the following occurs: 1) the subject continues on commercial BG00012 following study withdrawal/completion, or 2) the subject is initiated on another MS disease-modifying therapy.

LLN = lower limit of normal; MS = multiple sclerosis.

¹ Lymphocyte counts \geq LLN at 2 consecutive visits are required.

While dosing is withheld, subjects will continue tests and assessments according to [Table 1](#) (and may also undergo additional assessments to evaluate the laboratory abnormality as per the Investigator's standard practice). In addition, subjects (whether on study treatment, having dosing temporarily withheld, or permanently discontinued) must have the abnormal laboratory result rechecked at the central laboratory as follows:

- For all analytes, with the exception of lymphocytes, results will be rechecked at least every 2 weeks until resolution or stabilization of the laboratory value. Depending on the severity and clinical significance of the abnormality, the Investigator may need to perform the retests more frequently.
- For lymphocytes, results will be rechecked at least every 4 weeks for 24 weeks and then every 3 months (**unless clinically indicated more often or at the Investigator's discretion**) until the lymphocyte count is \geq LLN or for 52 weeks after the last dose, or until one of the following occurs: 1) the subject continues on commercial BG00012 following study withdrawal/completion, or 2) the subject is initiated on another MS disease-modifying therapy. Depending on the severity and clinical significance of the abnormality, the Investigator may need to perform the retests more frequently.

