¹ An Unscheduled Relapse Assessment Visit will be conducted within 72 hours of symptom onset of a suspected relapse (i.e., new or recurrent neurologic symptom[s]).

² Discontinuation refers to discontinuation of study treatment. Withdrawal refers to withdrawal of subjects from the study. The Discontinuation/Withdrawal Visit should be conducted as soon as possible and no later than 4 weeks after the last dose of study treatment.

CONFIDENTIAL

The information contained herein may not be used, disclosed, or published without the written consent of Biogen MA Inc.

³ Subjects who complete, temporarily withhold, or permanently discontinue study treatment for any reason and have a lymphocyte count <LLN will continue protocol-required visits and assessments and be followed every 4 weeks for 24 weeks and then every 3 months (**unless clinically indicated more often or at the Investigator's discretion**) until the lymphocyte count is \geq LLN or for 52 weeks after the last dose, or until one of the following occurs: 1) the subject continues on commercial BG00012 following study withdrawal/completion, or 2) the subject is initiated on another MS disease-modifying therapy. Note: lymphocyte counts \geq LLN at 2 consecutive visits are required.

⁴ Vital signs include body temperature, pulse rate, and systolic/diastolic blood pressure measurements.

⁵ Hematology testing must be performed every 4 weeks in subjects with lymphocyte count <LLN.

⁶ Study treatment must be temporarily withheld or permanently discontinued if any of the laboratory values meet the criteria defined in the protocol.

⁷ For females of childbearing potential.

⁸ Urine cytology must be performed if a subject experiences hematuria (of unknown etiology) at 2 consecutive visits or at the Unscheduled Relapse Assessment Visit or the Discontinuation/Withdrawal Visit.

⁹ An MRI must not be performed within 30 days of receiving a course of steroids.

¹⁰ A brain MRI scan will be performed unless assessed in the last 30 days.

CONFIDENTIAL

The information contained herein may not be used, disclosed, or published without the written consent of Biogen MA Inc.

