11.2.5. Treatment Schedule for Subjects With Abnormal Lymphocyte Count

11.2.5.1. Schedule for Subjects With Lymphocyte Count $<500/\text{mm}^3$

BG00012 must be permanently discontinued when the lymphocyte count meets the threshold limits defined in [Table 5](#).

CONFIDENTIAL

The information contained herein may not be used, disclosed, or published without the written consent of Biogen MA Inc.

Table 5: Lymphocyte Count Criteria Requiring Permanent Discontinuation of BG00012 Treatment

Laboratory Parameter	Laboratory Result	Required Action
Lymphocyte count	<500/mm ³	The Investigator should repeat the test as soon as possible. If retest confirms that lymphocyte count is <500/mm ³ , lymphocyte count should be closely monitored (at least every 4 weeks). If lymphocyte count is <500/mm ³ for more than 6 months, study treatment must be permanently discontinued.

If study treatment is permanently discontinued due to lymphocyte count <500/mm³, subjects may continue protocol-required tests and assessments and also undergo lymphocyte follow-up every 4 weeks for 24 weeks and then every 3 months (**unless clinically indicated more often or at the Investigator's discretion**) until the lymphocyte count is \geq LLN or for 52 weeks after the last dose, or until one of the following occurs: 1) the subject continues on commercial BG00012 following study withdrawal/completion, or 2) the subject is initiated on another MS disease-modifying therapy [see [Table 2](#)]. During the lymphocyte follow-up, if the lymphocyte count does not recover to above LLN after 24 weeks, the treating neurologist should contact the Medical Monitor.

11.2.5.2. Schedule for Subjects Who Complete, Temporarily Withhold, or Permanently Discontinue Study Treatment for Any Reason and Have a Lymphocyte Count <LLN

Subjects who complete the 96-week treatment period and who have a lymphocyte count <LLN will be followed every 4 weeks for 24 weeks and then every 3 months (**unless clinically indicated more often or at the Investigator's discretion**) until the lymphocyte count is \geq LLN or for 52 weeks after the last dose, or until one of the following occurs: 1) the subject continues on commercial BG00012 following study withdrawal/completion, or 2) the subject is initiated on another MS disease-modifying therapy. During the lymphocyte follow-up, if the lymphocyte count does not recover to above LLN after 24 weeks, the treating neurologist should contact the Medical Monitor.

[figure not shown]

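### For subjects still on drug, Section 11.2.1 lets lymphocyte rechecks drop to 3-monthly after 24 weeks while Tables 4 and 5 keep them at least 4-weekly; detection of the mandatory stop could nominally come 0, 4 or 8 weeks later

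*Protocol*

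**What the plan says.** Only protocol version 3.0 is used here. Five places bear on a subject with a low lymphocyte count who is still on drug.

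- **Table 4, on-treatment row for counts below LLN (Section 11.2.1).** After a confirming retest, "lymphocyte count should be closely monitored (at least every 4 weeks"). There is no step-down. A separate row, for subjects who complete, withhold or discontinue drug, carries the step-down to 3-monthly testing after 24 weeks.
- **Table 5, counts below 500/mm³ (Section 11.2.5.1).** The same 4-weekly minimum, again with no step-down. If the count stays below 500/mm³ "for more than 6 months, study treatment must be permanently discontinued".
- **Table 2, footnote 5 (Section 4.2).** "Hematology testing must be performed every 4 weeks in subjects with lymphocyte count <LLN", with no step-down and no limit by treatment status.
- **Section 11.2.1, text after Table 4.** The lead-in to the recheck bullets says "subjects (whether on study treatment, having dosing temporarily withheld, or permanently discontinued) must have the abnormal laboratory result rechecked". The first bullet excludes lymphocytes. The second covers them: "results will be rechecked at least every 4 weeks for 24 weeks and then every 3 months", with the qualifier "unless clinically indicated more often or at the Investigator's discretion".
- **Section 10.1.** The stop for a count below 500/mm³ is worded "for 6 months as outlined in" Tables 4 and 5.

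**The concern.** The lead-in puts on-drug subjects under the bullet, and the bullet then allows a longer test interval than Tables 4 and 5 allow for the same subjects. A site that follows the bullet literally complies with Section 11.2.1 and breaches Table 5.

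The timing makes this more than untidy wording. The mandatory stop can be detected only by a count taken after 6 months, and the bullet relaxes the interval at 24 weeks, shortly before that point. The protocol itself reports, in Section 5.3.2, that progressive multifocal leukoencephalopathy has occurred with severe, prolonged lymphopenia. This is a pediatric study whose primary objective is long-term safety, so detection of a mandatory safety stop should not depend on which passage a site reads.

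**Working it through.** The documents give no figure for detection delay, so there is none to reproduce. The check is calendar arithmetic.

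**Inputs**
- Six months: 6 × 365.25/12 = 182.6 days; 182.6/7 = 26.1 weeks.
- Three months: 3 × 365.25/12 = 91.3 days; 91.3/7 = 13.0 weeks.
- Tables 4 and 5: tests at 4, 8, …, 24, 28, 32, … weeks.
- Section 11.2.1 bullet: tests at 4, 8, …, 24 weeks, then every 13.0 weeks.
- Routine hematology in protocol Table 1: study Weeks 12, 24, 36, 48, 60, 72, 84 and 96, so every 12 weeks.
- Assumption: week 0 is the first count below 500/mm³, both for the bullet's 24 weeks and for the 6-month clock. The protocol defines neither start for a subject on drug.

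**Step 1. Where the step-down falls.** 26.1 − 24 = 2.1. The bullet's 4-weekly phase ends about 2 weeks before the threshold.

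**Step 2. Tables 4 and 5.** The first test after 26.1 weeks is at 28 weeks, which is 28 − 26.1 = 1.9 weeks past the threshold.

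**Step 3. The bullet with nothing else.** The next required test is at 24 + 13.0 = 37.0 weeks, about 11 weeks past the threshold and 37 − 28 = 9 weeks later than under the Tables. From after week 24 up to week 52 the Tables require 7 tests (28, 32, …, 52) and the bullet requires 2 (about 37 and 50).

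**Step 4. The bullet plus routine hematology.** Subjects on drug also have the Table 1 tests. On a 4-week grid the first low count can fall in three positions:

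| First count below 500/mm³ | Routine tests, weeks after it | First required test past 26.1 weeks | Same, Tables 4 and 5 | Later by |
|---|---|---|---|---|
| At a routine visit | 12, 24, 36 | 36 | 28 | 8 weeks |
| 4 weeks after one | 8, 20, 32 | 32 | 28 | 4 weeks |
| 8 weeks after one | 4, 16, 28 | 28 | 28 | 0 weeks |

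Measured from the threshold, the lag is 9.9, 5.9 or 1.9 weeks, against 1.9 weeks under the Tables. These are nominal dates; visits have a window of ±5 days.

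**Step 5. Sensitivity to the start points.**
- If the 6-month clock starts at a confirming retest 1 week later, the threshold is 27.1 weeks and the tests in Step 4 do not change.
- If it starts 2 weeks later, the threshold is 28.1 weeks. The Tables' first test is then at 32 weeks. The bullet plus routine tests gives 36, 32 or 37 weeks in the three positions, so 4, 0 or 5 weeks later.
- If the bullet's 24 weeks runs from the first count below LLN, the step-down could come before the count falls below 500/mm³, leaving fewer required tests inside the 6-month window.

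**Step 6. Section 10.1 wording.** On the 4-weekly grid no test falls at 26.1 weeks. Whether the rule is 6 months or more than 6 months, the first test that can trigger it is at 28 weeks.

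**The case against.** The strongest reply is that the bullet was never meant for subjects on drug. Its end points are 52 weeks from the last dose, a move to commercial drug once the study is over, or a start on another MS therapy. None of these fits a subject still taking study drug; only recovery to LLN does. The wording closely follows the Table 4 row for subjects off drug. The provisions written specifically for on-drug subjects, Table 4's first row and Table 5, agree with each other. The bullet is also a minimum that twice allows more frequent testing, so a site testing every 4 weeks satisfies every passage. Table 2 footnote 5 sits in a table of additional visits, so it is supporting evidence rather than the main on-treatment rule.

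Much of this stands as an account of intent. It does not remove the conflict. The lead-in names on-treatment subjects, the other bullet excludes lymphocytes, and permission to test more often is not a requirement.

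Three stronger readings are tempting but not supported:

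- **That on-drug testing simply becomes 3-monthly, with detection 9 weeks later.** This ignores the qualifier and the 12-weekly hematology in Table 1. At nominal dates the added delay is at most 8 weeks.
- **That on-treatment lymphocyte data would be uneven between sites.** SAP 6.3.2.3 summarizes counts by timepoint, and SAP 6.1.7 uses ±5-day windows with the observation closest to target. Extra tests at, say, study Week 28 or 32 fall outside those windows. Post-treatment counts and time to recovery do not depend on on-drug frequency.
- **That Section 10.1 sets a different stop.** It defers to Tables 4 and 5, and Step 6 shows no practical difference on a 4-weekly grid.

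**Conclusion.** The point holds as an internal inconsistency that affects a safety stop. It is not a deliberate design choice: the text reads most naturally as off-drug wording placed under too broad a lead-in. Protocol version 3.0 nevertheless gives two minimum recheck frequencies for the same on-drug subjects, and they part about 2 weeks before the 6-month threshold.

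Detection of the mandatory stop is nominally 0, 4 or 8 weeks later under the bullet plus routine hematology than under Tables 4 and 5. Eight weeks applies when the first low count falls at a scheduled visit. The figures assume that the 24 weeks and the 6-month clock both start at the first count below 500/mm³, that visits fall on their nominal dates, and that the site does no more than the bullet requires. Starting the 6-month clock at a retest 2 weeks later changes them to 4, 0 or 5 weeks.

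How many subjects would be affected is unknown. Section 8.2 excludes counts below 500/mm³ at entry, and the documents give no expected incidence. The analysis of the primary endpoint does not change.

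**What to change.** Reconcile the Section 11.2.1 lead-in and lymphocyte bullet with Tables 4 and 5 and with Table 2 footnotes 3 and 5. Footnote 3 steps down after 24 weeks for subjects off drug or with drug withheld, and footnote 5 does not step down for anyone below LLN, so those two need to be read together as well. State:

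1. which recheck frequency applies on drug, with drug withheld, and off drug;
2. which event starts the 24 weeks;
3. which event starts the 6-month clock for the stop.

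The clinical team decides the rule; the statistical request is only that there be one. As a minor tidy-up, align the duration wording in Section 10.1 with Tables 4 and 5.

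The cost is protocol wording, plus a matching edit to the SAP's copy of the Table 2 footnotes if those change. No endpoint, analysis or sample size is affected.

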11.2.2. Resumption of Study Treatment Dosing

Resumption of BG00012 treatment is to be considered on a case-by-case basis and must be discussed with the Medical Monitor.

CONFIDENTIAL

The information contained herein may not be used, disclosed, or published without the written consent of Biogen MA Inc.

Resumption of study treatment after an interruption

Subjects who are allowed to resume BG00012 dosing after an interruption of ≥ 2 weeks will restart dosing at a reduced dosage for 1 week. Subjects will take one 120-mg capsule BID for 1 week. After 1 week at the reduced dose, subjects will resume taking two 120-mg capsules BID.

11.2.3. Subsequent Development of Additional Laboratory Abnormalities

Subjects who subsequently develop the same abnormal laboratory value at any other time during the study must permanently discontinue dosing with BG00012, i.e., only 1 dosing interruption is allowed for each subject for the same laboratory abnormality. However, subjects who subsequently experience a different laboratory abnormality can have study treatment withheld again. For example, if a subject had dosing temporarily withheld for an abnormal ALT, then had dosing resume after ALT returned to acceptable limits, and subsequently developed abnormal WBCs, then the subject may have BG00012 withheld again. However, only 2 dosing interruptions are allowed for each subject.

Any subject who experiences abnormal laboratory results (which meet the criteria defined in [Table 3](#)) on a third occasion must discontinue dosing for the remainder of the study.

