6. STUDY OBJECTIVES AND ENDPOINTS

6.1. Primary Objective and Endpoint

The primary objective of the study is to evaluate the long-term safety of BG00012 in subjects who completed Study 109MS202.

The primary endpoint that relates to this objective is the incidence of AEs, serious AEs (SAEs), and discontinuations of study treatment due to an AE.

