15.1. Definitions

15.1.1. Adverse Event

An AE is any untoward medical occurrence in a patient or clinical investigation subject administered a pharmaceutical product and that does not necessarily have a causal relationship with this treatment. An AE can therefore be any unfavorable and unintended sign (including an abnormal laboratory finding), symptom, or disease temporally associated with the use of a medicinal (investigational) product, whether or not related to the medicinal (investigational) product.

Determination of whether an abnormal laboratory value meets the definition of an AE will be made by the Investigator. Although abnormal laboratory values are typically not considered AEs, the following considerations may result in an abnormal laboratory value being considered an AE:

- A laboratory test result that meets the criteria for an SAE
- A laboratory test result that requires the subject to receive specific corrective therapy
- A laboratory abnormality that the Investigator considers to be clinically significant

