### **6.3.2.2 Clinical Adverse Events**

Treatment (BG00012)-emergent AEs are defined as AEs occurring or worsening after beginning study treatment (after the first dose in study 109MS311).

Incidence of AEs will be summarized using frequency distribution tables; overall, by severity, and by relationship to BG00012. The summary tables will include incidences for system organ class as well as for preferred terms within each system organ class. Similar incidence analyses will be summarized for SAEs and for the most common AEs.

AEs will be coded using the MedDRA dictionary (version 20.1). This coding system provides five levels to classify AEs. In general, AEs will be presented by system organ class and preferred term.

The summary tables will include incidence estimates for overall system organ class as well as for preferred terms within each system organ class. AEs will be presented in the order of decreasing incidence of system organ class and then by preferred term within system organ class.

If a subject experiences an event more than once during the study, he/she will be counted only once using the maximum severity if more than one severity is reported, within each system organ class/preferred term.

AEs will be classified by severity (mild, moderate and severe) and by relationship to BG00012.

The incidence of SAEs will be presented by system organ class and preferred term. Details of each SAE will be listed, including subject ID, system organ class/preferred term, date of onset, severity, relationship to BG00012 and action taken. Subject narratives will also be provided.

The incidence of AEs that led to early withdrawal from the study will be presented separately. A listing of the individual subjects with these AEs will also be presented.

The incidence of AEs that led to treatment discontinuation during the study will be presented in a separate table, along with a listing of these individual subjects who experienced AEs leading to treatment discontinuation.

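### The mandated stop for lymphocytes below 500/mm³ for more than 6 months has no AE-recording instruction, so it enters the primary count of AE discontinuations only at the Investigator's discretion

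*Protocol*

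**What the plan says.** The primary endpoint (Protocol 6.1) has three components, one of which is "discontinuations of study treatment due to an AE". For that component SAP 6.3.2.2 says: "The incidence of AEs that led to treatment discontinuation during the study will be presented in a separate table".

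The protocol mandates permanent laboratory stops in three places.

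- **Section 11.2.1, Table 3** (AST/ALT, creatinine, WBC, hematuria). If the abnormality lasts at least 4 weeks off drug, or urine cytology is positive, "then the subject must permanently discontinue study treatment, and the event must be recorded as an AE".
- **Tables 4 and 5** (Sections 11.2.1 and 11.2.5.1). If lymphocytes are below 500/mm³ "for more than 6 months, study treatment must be permanently discontinued". Neither table mentions an AE.
- **Section 11.2.3.** A subject who develops the same abnormality again "must permanently discontinue dosing with BG00012, i.e., only 1 dosing interruption is allowed for each subject for the same laboratory abnormality", and a subject who meets the Table 3 criteria "on a third occasion must discontinue dosing for the remainder of the study". Neither rule mentions an AE.

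The general rule is in Section 15.1.1, where the Investigator decides: "Although abnormal laboratory values are typically not considered AEs, the following considerations may result in an abnormal laboratory value being considered an AE". The three considerations are meeting SAE criteria, needing specific corrective therapy, and "A laboratory abnormality that the Investigator considers to be clinically significant".

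Section 10.1 lists the lymphocyte stop and the other laboratory stops as discontinuation reasons in their own right, requires the reason on the eCRF, and lets subjects who stop drug stay in the study. SAP 6.1.2 plans counts of subjects completing treatment and of subjects discontinuing before Week 96, but asks for a reason only in connection with early withdrawal.

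**The concern.** The AE-discontinuation count is built from AE records alone. Where the protocol forces a permanent stop without requiring an AE record, whether the stop is counted depends on one Investigator's judgment. Two sites with the same 6-month lymphopenia stop could contribute different data to the primary endpoint, both fully compliant.

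The lymphocyte stop is the one with substance. Protocol 5.3.2 reports progressive multifocal leukoencephalopathy in the setting of severe, prolonged lymphopenia, and that is the state the 6-month rule addresses. In a long-term pediatric safety study, a reader of the AE-discontinuation table would expect a mandated stop for that condition to be in it.

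**Working it through.** The documents state no sample size, event rate or target for this endpoint, and SAP 6.1 plans descriptive statistics only, so there is no planned figure to reproduce. The check is a trace of each mandated permanent laboratory stop to its AE instruction, in protocol version 3.0.

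| Mandated permanent stop | AE record required? | In the AE-discontinuation count? |
|---|---|---|
| Table 3: AST/ALT, creatinine or WBC abnormal ≥4 weeks off drug | Yes | Yes |
| Table 3: hematuria ≥4 weeks off drug, or positive cytology | Yes | Yes |
| Tables 4 and 5: lymphocytes <500/mm³ for more than 6 months | No | Only if the Investigator records an AE |
| 11.2.3: same abnormality recurs | Not by 11.2.3 | As Table 3 if it lasts ≥4 weeks or cytology is positive; otherwise at discretion |
| 11.2.3: third occasion | Not by 11.2.3 | As the row above |

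All 4 Table 3 parameters carry the AE clause; none of the 3 other stop rules does.

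**How wide each gap is.** Table 3 has no lymphocyte row, so a low lymphocyte count alone never triggers the AE clause, however long it lasts. (A WBC count that also meets the Table 3 criterion would trigger it through the WBC row.) The 11.2.3 gap needs a chain of events: a confirmed abnormality, a hold, a resumption discussed with the Medical Monitor (11.2.2), a recurrence or third occasion within 96 weeks, resolution in under 4 weeks, and an Investigator who does not call it an AE.

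**Whether another rule closes it.** A mandated stop of study drug is not among the three considerations in Section 15.1.1. Section 15.3.1 requires every AE to be recorded, but only once the event has been judged an AE.

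**Where the stop shows up otherwise.** Protocol Table 2 and the matching SAP table define discontinuation as stopping study treatment and withdrawal as leaving the study. On those definitions, the SAP 6.1.2 counts of subjects completing treatment and discontinuing before Week 96 should include these stops. The reason is attached only to early withdrawal, so a subject who stops drug and stays in the study has no clearly tabulated reason. SAP 6.3.2.3 summarizes laboratory values and lymphocyte recovery, but not discontinuations.

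**Size.** With k uncounted stops among N treated subjects, the reported incidence falls by k/N. N is assumed, because the documents give none. If there is no other AE discontinuation, the report reads 0/N where a full count would read k/N. Exact (Clopper-Pearson) 95% limits are given for illustration only.

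| Assumed N | Reported 0/N | One stop counted, 1/N | Two stops counted, 2/N |
|---|---|---|---|
| 20 | 0% (0–16.8) | 5% (0.1–24.9) | 10% (1.2–31.7) |
| 50 | 0% (0–7.1) | 2% (0.1–10.6) | 4% (0.5–13.7) |
| 100 | 0% (0–3.6) | 1% (0.0–5.4) | 2% (0.2–7.0) |

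**The case against.** The best defense is that a route to an AE record already exists. Section 15.1.1 counts an abnormal laboratory finding as a possible AE and names clinical significance as a ground. Six months of lymphocytes below 500/mm³, ending in loss of treatment, is an obvious candidate, and nothing in the documents suggests that Investigators would judge otherwise. That stands as far as it goes: what is missing is an automatic trigger. But the protocol did not rely on judgment for any Table 3 stop, and it gives no reason for relying on it here.

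For Section 11.2.3 the defense is stronger. Table 3 sets the mandatory AE record at 4 weeks' persistence, and a value that normalizes quickly, where drug stops only because the permitted interruption has been used, is not self-evidently a discontinuation due to an AE. Leaving those cases to the Investigator is a defensible design choice.

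A reader might also infer that lymphopenia stops would go unseen. The documents do not support that. Low counts are retested within 2 weeks and then checked at least every 4 weeks; follow-up runs for up to 52 weeks after the last dose, with Medical Monitor contact if there is no recovery after 24 weeks; an IDMC reviews interim safety data (19.2.2); and SAP 6.3.2.3 summarizes lymphocyte counts and time to recovery. What can be missing is the entry in the AE-discontinuation table and a tabulated reason for stopping drug.

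Finally, the arithmetic above shows the effect of one or two uncounted stops, not how likely they are.

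**Conclusion.** The point holds, mainly for the lymphocyte stop. A mandated permanent stop for prolonged lymphopenia counts toward a primary-endpoint component only if the Investigator judges it an AE, whereas every Table 3 stop must be recorded as one. For Section 11.2.3 it holds only where the abnormality resolves in under 4 weeks without positive cytology; it would be wrong to read it as covering all recurrence or third-occasion stops.

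The number of subjects affected cannot be derived from the documents and is probably small. One uncounted stop is worth 5, 2 or 1 percentage points at an assumed N of 20, 50 or 100. In a descriptive safety report the practical difference is between stating no such discontinuation and stating one. The conclusion assumes that the eCRF completion instructions, which are not among the documents, do not already require an AE record for these stops.

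**What to change.** **Main change, SAP only.** In 6.1.2, tabulate permanent discontinuations of study treatment by reason, separately from withdrawal from the study. In 6.3.2.2, place beside the AE-discontinuation table a count of all permanent stops mandated by laboratory criteria (Tables 3 to 5 and Section 11.2.3), split by whether an AE was recorded. Section 10.1 already requires the reason on the eCRF, so no new data are needed. If the eCRF categories do not identify laboratory stops, the few cases can be classified from the recorded reason and the laboratory results.

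**Secondary change, at the next protocol amendment.** Add the Table 3 AE instruction to the 6-month lymphocyte stop in Tables 4 and 5. Leave the AE status of transient 11.2.3 stops to the Investigator; the SAP table will show them in any case.

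**Cost.** One extra table and possibly a slightly higher reported incidence of AE discontinuations. The protocol clause is likely to need ethics committee approval under Section 19.3, with about 20 sites planned, so it should wait for an amendment made for other reasons. No stopping threshold, test or visit changes.
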